Height, weight, waist circumference, hip circumference, and blood pressure will be collected before blood draw. Weight will be assessed on an electrical impedance scale (TANITA) to simultaneously estimate body composition (% body fat). Two readings will be taken, and the average of both used for analyses.

Participants will next be relocated to the neighboring Psychophysiology Laboratory (Presbyterian Hospital, 16th floor). As per CUIMC's workspace assessment, this space can comfortably accommodate 1 researcher and 1 patient. Furthermore, we will keep a window open to facilitate airflow, and designate one door to the lab as entrance and one as exit to ensure safe traffic flow.

The study nurse will insert a venous catheter in the antecubital vein to draw blood amounting to 100 mL. This includes one EDTA coated tube (2mL), two Serum Separation Tubes (5mL), and five Buffered Sodium Citrate tubes (2.7mL) for complete blood count on whole blood and two for plasma (8mL), two non- coated tubes for serum (8mL) and five Acid Citrate Dextrose tubes (8.5mL) for cells to be used to assess mitochondrial function. Allostatic load biomarker analyses will be performed on plasma and serum.

Cheek swab: A cheek swab (MasterAmp™ Buccal Swab Brush) of the internal mucosa from both cheeks will be performed to collect DNA. This procedure takes approximately 5 seconds and is painless. Participant will pull down their face mask for the duration of this cheek swab. Collected material will enable the measurement of mtDNA copy number, DNA methylation, and mtDNA mutation heteroplasmy in a

Protocol Summary Form

somatic tissue.

Breakfast: Following blood draw and anthropometric measurements, participants will break their fast with a standardized continental breakfast in accord with any

dietary restrictions (gluten intolerance, etc.) ascertained beforehand on a standardized menu. Participant will eat alone with face covering removed.

Participants will be suggested to go for a bathroom break before the next part. **Clip of hair:** A small clip of hair is collected from the back of the head to measure cumulative levels of steroid hormones (cortisol, sex hormones, endocannabinoids). Two small bundles of approximately 100-200 hairs each (a few millimeters) are clipped near the scalp, just below the cranial bone. The instructions are attached with this protocol (Appendix #1.2). Analyses will be performed by our collaborator [name] (Technische Universität Dresden, Germany).

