Mitochondrial Stress, Brain Imaging, and Epigenetics (MiSBIE)

NCT04831424
October 6, 2023

Lay Summary of Proposed Research

Age-related physical and cognitive decline, as well as the risk of neurological diseases, are increased by the effects of psychosocial stress. Psychosocial stress triggers neuroendocrine, metabolic, cardiovascular, and inflammatory changes in the body. These changes vary in nature and magnitude between individuals, and are associated with long-term disease risk. However, the biological determinants of the stress response are not well understood. Why do some individuals respond more strongly than others to the same stressor?

Our preclinical studies in mouse models with dysfunctional mitochondria, a cellular organelle which produces energy and signals of adaptation, indicate that mitochondria regulate how different organ systems and major stress response axes are activated during psychological stress. This project aims to translate this discovery in a population of individuals with varying degree of mitochondrial dysfunction, and to test potential neural mechanisms. This study will take place at Columbia University Irving Medical Center (CUIMC) and the Mortimer B. Zuckerman Mind Brain Behavior Institute (ZMBBI) and will recruit patients with genetic mitochondrial disease and healthy controls.

Each participant will be studied over two days. On Day 1, we propose to monitor dynamic changes in different hormones and molecules in blood (catecholamines, inflammatory cytokine interleukin 6) and saliva (cortisol) in response to a standardized laboratory "stressor". Participants will also undergo a medical assessment. On Day 2, we propose to examine whether these changes are mediated by inter-individual differences in functional connectivity among different brain regions measured by functional magnetic resonance imaging (fMRI).

Participants will also complete a questionnaire package to evaluate psychosocial functioning and clinical disease severity as well as undergoing a neuropsychological assessment. This interdisciplinary project leverages access to a unique population of patients with genetically

Protocol Summary Form

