Multi-systemic dysregulation can arise from peripheral alterations of specific organ functions, such as the adrenal glands, the liver, peripheral nerve function, or the cardiovascular system. Alternatively, maladaptive neuroendocrine, metabolic, and epigenetic profiles may be driven by abnormal central nervous system functions, including resting brain connectivity and activation patterns during stressful situations. Thus, the brain is understood to play a central role in stress- related pathogenesis (45). To date, however, neither brain connectivity nor activation has been examined in patients with mitochondrial disease. The proposed study will be the first study to assess the pathways linking mitochondrial dysfunction to stress pathophysiology, and to identify candidate neural regulatory mechanism to explore further. This would provide us with unique insights into the long-standing question of how psychosocial stress 'gets under our skin and skull'.

To study the potential role of the brain as a driver of abnormal stress reactivity, we therefore plan to use functional magnetic resonance imaging (fMRI) and multivariate analyses to test a mediation model where abnormal stress perception caused by mitochondrial dysfunction occurs at the level of the brain and drives abnormal allostatic and epigenetic responses peripherally. This study will thus begin to untangle the role of central nervous system *vs* peripheral physiological processes in mitochondrial disease, allowing us to explore a previously unrecognized sub- cellular mitochondrial pathophysiological mechanism.

Deciphering the role of mitochondrial dysfunction and the mechanism(s) by which it alters stress physiology and is transduced into allostatic load is not only directly relevant to mitochondrial disease, but also to a greater spectrum of neurodegenerative disorders where both life stress (46, 47) and mitochondrial dysfunction (48, 49) have been implicated, including Alzheimer disease, Parkinson disease, schizophrenia, and depression. In addition, this will be the first study to examine the relations between mitochondria, epigenetic changes, and brain activation. At the end of this study, we will have identified candidate molecular, neuroendocrine, and neural mechanisms that can be further investigated in clinical populations and mechanistically explored further in animal models.

Specific Aims and Hypotheses

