exaggerated epigenetic responses to stress. We will isolate sub-types of peripheral blood mononuclear cells at baseline to map genome-wide cytosine methylation levels. Pre- and post-stress blood samples will also be collected to track stress reactive differences by pyrosequencing of target genes linked to stress regulation and brain remodelling. Results from this aim will complement those of Aim 1 by defining stress reactivity at the sub-cellular, molecular levels.

Aim 3: Map brain-wide neural connectivity patterns in m.3243A>G and single mtDNA deletion patients, and determine if this mediate abnormal peripheral stress reactivity.

Combining measurements of peripheral stress physiology with functional neuroimaging (fMRI-BOLD), our team and others have shown that neuroendocrine, inflammatory, and cardiovascular reactivity to stress can be predicted from discrete

activation patterns among specific brain regions in healthy adults. Furthermore, the brain is an organ primarily affected in mitochondrial diseases and functional connectivity is sensitive to energetic defects, but the nature and impact of these alterations in human mitochondrial disease is unknown. *We hypothesize that patients with mitochondrial defects will exhibit abnormal patterns of resting state and task- elicited neural connectivity, including the executive network, which will statistically mediate alterations in physiological stress reactivity.* On a second visit (Day 2), we will perform structural and functional whole-brain neuroimaging of default mode network and tasks selected to match the stress reactivity on Day 1.

Taken together, this translational study will establish how neural connectivity is altered in mitochondrial disease, and begin to untangle neural pathways that may translate mitochondrial dysfunction into abnormal physiological dysregulation. This study will be the first to test the role of mitochondria in mediating mind-body processes. The resulting papers will inform future work in various fields including clinical mitochondrial medicine and neurology, psycho-neuro-endocrinology, psycho- neuro- immunology, and psychosomatic medicine.

Aim 4: To establish the within-person and technical variability in key study outcomes, two healthy volunteers will “repeat” visits to obtain blood samples up to 10 timepoints over the study period.

To establish the within-person and technical variability in key study outcomes, we will

Protocol Summary Form

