The task instructions will be projected from a liquid crystal display projector zoomed to a screen inside the MR suite or viewed through dual channel binocular goggles. Functional fMRI-BOLD images will be acquired.

To account for the accessibility needs of patients with visual processing issues or ophthalmoplegia, instructions and text during scanning will be read aloud by the coordinator.

During each pause between acquisitions, the participant is asked to rate their physical discomfort on a scale of 0-10. If the score rises above 5, the coordinator pauses the session and asks if the participant wishes to continue or if any adjustments can be made (i.e. change in position, an additional blanket for warmth, a sitting break).

As on Day 1, at three time points during the MRI imaging session saliva samples will be collected, along with affect ratings (5 questions).

These fMRI tasks will be administered in the following order:

Saliva sample and affect rating #10

(A) *Localizer (1 run, 1 min)*

Localizing of brain and defining region of interest.

(B) *Field map (1 run, 1 min)*

Acquisition of field map for multiband correction.

(C) *T2 scan (1 run, 12 min)*

T2-weighted images for detection of potential lesions and ventricles. This scan will be collected as participants are instructed to "rest and allow their minds to wonder and not to think of anything in particular". Participants are also instructed not to fall asleep.

(D) *T1 structural scan (1 run, 5 min)*

T1-weighted images for anatomical co-registration. This scan will be collected as participants are instructed to "rest and allow their minds to wonder and not to think of anything in particular".

(E) *Multisensory (1 run, 5 min)*

Protocol Summary Form

Participants will be trained and later exposed to the multisensory task. This task consists of visual (checker board), auditory stimulation (constant pitch sound), button push on the button box.

(F) Resting State Run #1 (1 run, 11 min)

This scan will be collected as participants are instructed to “rest and allow their minds to wonder and not to think of anything in particular”. Participants are reminded not to fall asleep.

Saliva sample and affect rating #13

(G) N-back task Run #1 (1 run, 6 min)

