This working memory task (64) consists of 9 blocks presented in ABBA or BAAB order, interspersed by 25 s of resting fixation. On each of 360 trials, a word is presented for 2 s followed by an inter-stimulus-interval fixation cross for 1 s. Participants are instructed to respond as quickly and accurately as possible to each word with a button press indicating, “yes, this word matches the word presented n-trials ago” (a target response) or “no, this word does not match the one presented n-trials ago” (a nontarget response). The first 3 trials of each block are not included in the analysis; these trials are always nontargets in the 3-back block and therefore did not carry the same task demand as the remaining trials.

(H) N-back task Run #2 (1 run, 6 min)

This is the second run of the N-back task. Instructions are the same as in “G”.

(I) Socio-evaluative Task (1 run, 6 min)

The procedure will be the same as in day 1 except subjects will be told that their “performance on the first speech task was slightly below average when compared with other participants’ speeches” and participants will be asked to “try to be more persuasive when delivering this speech”. They will be told that the speech will be delivered after the scan session to the expert who evaluated you yesterday. At the end of the task, participants will be told that they were randomly selected not to give their speech, as in previous work. A pulse oximeter will be hooked up to participants, and heart rate responses in conjunction with brain activation will be assessed

(J) Cold Pressor Task (1 run, 6 minutes)

This is a modified task from the cold pressor administered on Day 1. Participants will be instrumented with a thermal arm wrap designed specifically for the MRI environment and will be instructed as follows: “We will place this arm wrap around your hand and arm. It is quite cold and may be uncomfortable, but it will not injure you.” The arm wrap is a fabric-based foldable unit fitted with Velcro attachments

for detachable gel packs, which are kept in a temperature-controlled freezer prior to the procedure. Five (5) minutes before the procedure, gel packs are removed from the freezer, attached to the arm wrap, and layered with two layers of waterproof film paper to adjust immediate contact temperature to safe but uncomfortable -2 ± 2 degrees Celsius, as previously described (65, 66).

(K) Diffusion Tensor Imaging – DTI (Seq 1-2, 6 min)

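### Aim 3 measures its brain mediator on Day 2, after the Day 1 stress response it is meant to explain, so the planned mediation can reflect the reverse path and should be reported as association

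*Protocol*

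**What the plan says.** The order of measurement is explicit. The protocol's Lay Summary places the response first: "On Day 1, we propose to monitor dynamic changes in different hormones and molecules in blood". It then says that on Day 2 "we propose to examine whether these changes are mediated by inter-individual differences in functional connectivity among different brain regions", where the changes referred to are those of Day 1. Aim 3 restates this as a hypothesis about resting-state and task-elicited connectivity, "which will statistically mediate alterations in physiological stress reactivity", and puts the imaging on the second visit. Study Procedures sets the two visits on consecutive days, and the SAP gives Day 1 as the time frame for cortisol and heart-rate reactivity.

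The direction of effect is also stated. Background, Significance, and Rationale describes a mediation model in which the abnormality "occurs at the level of the brain and drives abnormal allostatic and epigenetic responses peripherally".

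The Day 2 procedures are linked to Day 1. Aim 3 says the scanner tasks are chosen to match the Day 1 reactivity session. In Study Procedures, item 9, task (I) repeats the Day 1 speech procedure, after participants hear that their "performance on the first speech task was slightly below average", and task (J) is a modified form of the Day 1 cold pressor.

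Peripheral measures are also taken in the scanner. Under item 9, "at three time points during the MRI imaging session saliva samples will be collected", and for the speech task "heart rate responses in conjunction with brain activation will be assessed". Neither is named as the outcome of the mediation model. The SAP lists five outcomes and has no imaging or mediation analysis. Neither document gives a reverse-order model, a sensitivity analysis for this question, or an assumption that Day 2 connectivity is a stable trait.

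**The concern.** A mediator should precede the outcome it explains. Here each participant's outcome is complete a day before the mediator is measured, and some of the mediator is recorded during repeats of the tasks that produced the outcome. Someone who reacted strongly on Day 1 may respond differently to the same kind of task on Day 2. The causal arrow could then run from group to Day 1 reactivity to Day 2 brain response, with nothing running from brain to reactivity.

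The interpretation of Aim 3 is at stake. Its purpose is to separate central from peripheral causes of abnormal stress physiology. A significant indirect effect would be read as evidence for a central cause, and the same data could arise from the opposite process.

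**Working it through.** Neither document gives a power, effect-size or sample-size figure for Aim 3, so there is no planned figure to reproduce. No estimator is named either. The check uses the standard linear model: regress M on X, then Y on X and M, and take the product of the two paths.

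**Closed-form illustration (both paths assumed).** X is group, Y is Day 1 reactivity and M is the Day 2 brain measure, all standardised. The data follow the reversed order, with no effect of M on Y:

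- Y = 0.4X + e, with var(e) = 1 − 0.16 = 0.84
- M = 0.5Y + u, with var(u) = 1 − 0.25 = 0.75

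The mediation model then gives:

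- path X to M: 0.4 × 0.5 = 0.20
- slope of Y on M given X: (0.5 × 0.84) / (0.25 × 0.84 + 0.75) = 0.42 / 0.96 = 0.4375
- indirect effect: 0.20 × 0.4375 = 0.0875
- proportion mediated: 0.0875 / 0.4 = 21.9%, against a true value of 0

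**How often the test would be significant.** The same reversed process was simulated with 90 patients and 100 controls (three patient groups of 30 completers and 100 control completers, from Description of Subject Population). Mediation was declared when both paths were significant at two-sided 0.05, with 2,000 runs per cell. Group effects of 0.27 and 0.52 SD are the sizes the SAP reports for heart-rate elevation and allostatic load. They serve only as anchors, since they belong to other analyses; 0.80 SD is assumed. The within-group correlation r between Y and M is also assumed.

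| Group effect on Y | r = 0.2 | r = 0.3 | r = 0.5 | r = 0.7 |
|---|---|---|---|---|
| 0.27 SD | 6% | 10% | 17% | 25% |
| 0.52 SD | 10% | 18% | 43% | 71% |
| 0.80 SD | 16% | 37% | 77% | 97% |
| Mean false proportion mediated (about) | 4% | 9% | 25% | 49% |

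With 60 patients (Groups 1 and 2 only) against 100 controls at 0.52 SD, the rates are 6%, 15%, 36% and 60%. With no group effect on Y the rate stays at about 5% or lower, and with r = 0 it is below 1%. The inflation therefore comes from the reversed path.

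**Can the data reveal the direction?** Model fit cannot. The two orderings have the same maximised log-likelihood (difference below 1e-12). The ambiguity is also symmetric: when the brain truly mediates (0.52 SD, 90 vs 100), the reverse-order model is significant in 20%, 44% and 71% of runs at r = 0.3, 0.5 and 0.7.

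**Would a Day 2 outcome settle it?** It removes the reversal of days but not confounding. With a common cause of brain measure and reactivity and no effect between them in either direction (0.52 SD, 90 vs 100), mediation is declared in 48%, 71% and 85% of runs at r = 0.3, 0.5 and 0.7.

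**The case against.** Measurement order is not causal order. If connectivity is a stable characteristic, a Day 2 scan can stand in for its value before the stressor. The Lay Summary's phrase about differences between individuals fits that reading, and Aim 3 uses cautious language about statistical mediation and beginning to untangle pathways. This has force for the resting-state run, which precedes the Day 2 speech feedback, though it still follows the Day 1 stressor. The trait assumption carries the argument, however, and it is neither stated nor tested.

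A reader might infer that the below-average feedback is what carries each person's Day 1 response into the scan. The text does not support that. The feedback reads as a fixed script given to everyone, and a constant does not by itself transmit individual differences. It is described only at task (I), after the resting-state and N-back runs. The reverse path rests on the visit order and the repeated tasks.

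A reader might also infer that Aim 3 cannot be supported at all, or that a specified model is known to give 22%. Neither follows. The size depends on assumed paths. A standardised group path of 0.4 is about 0.87 SD for near-equal groups (2 × 0.4 / √0.84), larger than either SAP anchor. At 0.27 SD and r of 0.2 to 0.3, false mediation appears in only 6% to 10% of runs.

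Finally, replacing the outcome with Day 2 reactivity may look like a complete remedy. Of the in-scan saliva samples placed in the task list (#10, #13 and #14), only #14 follows the speech and cold tasks, so it cannot separate them. No Day 2 blood draw is described, so catecholamines, cytokines and the epigenetic responses would drop out. Adjustment for Day 1 reactivity also works both ways. If Day 1 reactivity drives both Day 2 measures, adjusting correctly gives a zero indirect effect. If the brain truly mediates with the same 0.4 and 0.5 paths, adjusting in both equations cuts the group-to-brain path from 0.40 to 0.3125.

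**Conclusion.** The point holds for Aim 3. Its mediator is measured after its outcome, the result is given a causal direction, and a standard linear mediation model cannot distinguish that direction from the reverse. The false proportion mediated is about 22% under the assumed 0.4 and 0.5 paths. Across the simulated range it runs from about 4% to 49% as the correlation rises from 0.2 to 0.7. The concern is strongest for task-elicited measures and weaker for resting-state connectivity, which is defensible only under an explicit stable-trait assumption.

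These figures rest on the standard linear model and on assumed correlations. They show what could happen and do not estimate what the trial's data contain. None of the five SAP outcomes is affected.

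**What to change.** Specify the Aim 3 mediation analysis, naming the outcome and the day on which it is measured, and make three changes:

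1. Report the model with the Day 1 outcome as association, not as evidence that the brain drives the response. State the trait assumption wherever resting-state connectivity is the mediator.
2. Report the reverse ordering alongside it, with Day 1 reactivity as mediator of the group difference in the Day 2 brain measure. Add a sensitivity analysis for unmeasured mediator-outcome confounding. The paired fits show the ambiguity; they do not test which direction is true.
3. As a further sensitivity analysis, use in-scanner heart rate and saliva from Day 2 as the outcome, with and without adjustment for Day 1 reactivity.

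The cost is a weaker causal claim for Aim 3 and some extra analysis. No new visit or sample is needed. The Day 2 model covers heart rate and saliva only, with one listed in-scan saliva sample after the stressors and no blood markers, and it leaves confounding in place.
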